Appendix 3: Imputation of FiO₂ values

If the value of FiO₂ is missing when the type of low flow device and oxygen flow is given, the below values will be used as the value of FiO₂ in the analysis. For example if a subject at a visit has a low flow device type of "Open Mask" with oxygen flow of 5 L/min, for analysis purposes a value of 40(%) for FiO₂ will be used.

It should be noted that sites are permitted to enter a range of values. For example if a site states the subject is on a low flow nasal cannula with oxygen flow of 3, the site can enter a range of FiO₂ from 28 to 36. No adjustments will be made in the analysis for site entered values to align with the below literature. Sites are also permitted to enter values that are outside the values presented in the reference tables (for example nasal cannula > 15 L/min).

- **Low Flow Nasal Cannula (Simon et al., 2016)**

Oxygen Flow (L/min)	Fraction of Inspired Oxygen (%)
1	24
2	28
3	32
4	36
5	40
6-15	44

- **Low Flow Open Mask (Simon et al., 2016)**

Oxygen Flow (L/min)	Fraction of Inspired Oxygen (%)
1	24
2	28
3	32
4	36
5	40
6-7	50
8-15	60

- **Venturi Mask (Batool and Garg., 2017)**

Oxygen Flow (L/min)	Fraction of Inspired Oxygen (%)
2 (blue)	24
4 (white)	28
6 (orange)	31
8 (yellow)	35
10 (red)	40
15 (green)	60

- **Partial Rebreather Mask (Batool and Garg., 2017)**

Oxygen Flow (L/min)	Fraction of Inspired Oxygen (%)
6	60
8	70
10	80

- **Non-rebreather Mask (MEDEST, 2020)**

Oxygen Flow (L/min)	Fraction of Inspired Oxygen (%)
10-15 L/min	80-100
Both flaps removed	80-85
One flap removed	85-90
Both flaps in place	95-100

- **Small Diffuser (OxyMask) (Paul et al., 2009)**

Oxygen Flow (L/min)	Fraction of Inspired Oxygen (%)
1.5	25
2	30
2.5	37
3	42
5	58
10	74
15	80

Appendix 4: Blinded Data Review Meeting Specification

Details on which important Protocol deviations will lead to exclusion from the PP and other analysis considerations that must be discussed in a blinded manner will be documented in the "VCRC2108-C21008 Blinded Data Review Meeting Specification_v1.0".

VCRC2108-C21008
Blinded Data Review

Appendix 5: Endpoint Derivation Details

Endpoint	Calculation	Handling of Death	Handling of Missing Data
All-Cause Mortality (Primary Analysis)	Date of event is the date of death Subjects without event will be censored at the time of completion/study discontinuation	n/a	n/a
All-Cause Mortality (Sensitivity Analysis including Multiple Imputation)	Proportion of deaths is the number of subjects with an ordinal scale value of 8 at Day 60	n/a	Missing data at Day 60 will be imputed.
Time to Sustained hospital discharge (Primary Analysis)	Date of event is the last date of discharge (for initial hospitalization or re-hospitalization for COVID-19 reasons) as recorded on the hospitalization form for subjects. If a subject has the event and subsequently withdraws (for reasons other than death) the subject will be treated as having the event If subject does not have event prior to completion/discontinuation the subject is censored at date of completion/discharge (for reasons other than death)	Subjects are treated as worst case (Day 60 is value used in analysis)	n/a
Time to Sustained hospital discharge (Sensitivity Analysis including Multiple Imputation)	Date of event is the last date of discharge (for initial hospitalization or re-hospitalization for any reason) as recorded on the hospitalization form for subjects with no missing data. For subjects with missing data, such that the event occurs at an imputed visit (≤ 2 ordinal scale occurs after which all subsequent visits stay at ≤ 2), time to sustained discharge will be the relative day of the imputed visit. For subject with Imputed data, if subjects discharges prior to missing data being observed and imputed values indicate the subject stays discharged (≤ 2), the last date of discharge recorded in the hospitalization form will be used For subjects with no event based on imputed and missing data, subjects will be censored at date of completion/Day 60.	Subjects are treated as worst case (Day 60 is value used in analysis)	Missing data will be multiple imputed
Number of days oxygen free up to Day 29	Sum of all ordinal scale values of 1, 3, 4 up to Day 29	Death treated as -1	Missing data will be multiple imputed

[figure not shown]
[figure not shown]

Endpoint	Calculation	Handling of Death	Handling of Missing Data
Free of Respiratory Failure	Responder is defined as having an ordinal scale value of ≤ 5 at a visit	No special rules (death will be a non-responder as will have an ordinal scale value of 8)	Missing data will be multiply imputed
Subjects discharged from hospital and free of Supplemental Oxygen Use	Responder is defined as have a value of 1 on the adjusted ordinal scale at a visit	No special rules (death will be a non-responder as will have an ordinal scale value of 8)	Missing data will be multiply imputed
Subjects on Non-Invasive Mechanical Ventilation, Invasive Mechanical Ventilation, ECMO or with Supplemental Oxygen Use	Subjects with event has a score of ≥ 5 on the ordinal scale	No special rules (death will be a event as will have an ordinal scale value of 8)	Missing data will be multiply imputed
Subjects needing ICU stay	Subjects who have a record for ICU stay on the hospitalization CRF	Counted as in ICU from date of death	No
Subjects on Invasive or Mechanical Ventilation or ECMO	Subjects with event has a score of ≥ 7 on the ordinal scale	No special rules (death will be a event as will have an ordinal scale value of 8)	Missing data will be multiply imputed
Number of Respiratory Failure free days up to Day 60	Sum of all days where ordinal scale is ≤ 5 from Day 2 up to Day 29; Day 60. For days between Day 29 and Day 60 refer to Section 10.14.	Days from death treated as respiratory failure	Missing data will be multiply imputed
Duration of hospitalization	Duration: end date of hospitalization-start date of hospitalization +1 Sum all individual hospitalizations and re- hospitalization for COVID-19 together If a subject discontinues trial following discharge for reasons other than death, the duration will be calculated as normal and no additional days added If a subject discontinues prior to discharge 60 days will be used in the analysis	Subjects that die will be treated as in hospital from date of death	N

Endpoint	Calculation	Handling of Death	Handling of Missing Data
Duration of hospitalization (Sensitivity analysis)	
Duration: end date of hospitalization-start date of hospitalization +1;
 
Sum all individual hospitalization (including all re- hospitalization) together
 
If a subject has missing data following date of discharge and imputed values stay ≤2, then subject will not have any further days added to the duration.
 
If subject has missing data following date of discharge and imputed values are >2, the duration of hospitalization will be the sum of the observed durations plus the count of the days where the values are >2.
 
If subject has missing data and was not discharged, if the imputed values indicate no discharge then the subject will have a duration of hospitalization derived as: Day 60/study completion – start date of hospitalization +1
 
If subject has missing data and was not discharged and imputed values indicate discharge the subject will have a duration of hospitalization derived as:
 
relative day of last ordinal scale value >2 – start date of hospitalization +1.
 
If a subject has impute data indicating further hospitalizations following the initial discharge, the count of the days where the ordinal scale value is >2 will be summed together and added to the duration of the initial hospitalization.
	Subjects that die will be treated as in hospital from date of death	Y
Duration of ICU stay	End date of ICU stay -start date +1; sum individual together; discontinues in ICU considered in ICU from day of discontinuation if not in ICU at discharge then no additional days added; no ICU stay a value of 0 used	Subject will be considered in the ICU from the date of death	n/a
Duration of invasive ventilation or ECMO	End date of use-start date of use +1; sum together; discontinue while on, considered on from date of discontinuation; not on and discontinue will not have any other days; subjects with no use be 0	Subject will be considered on ECMO/ from the date of death	n/a

Signature /Date:	DocuSigned by:  8/24/2022 AC2E3DABD5E2467...
PRA/ICON plc.	
Biostatistician / Title:	[name] / Senior Biostatistician
Signature /Date:	DocuSigned by:  1B2ED5FAA2A54EF...

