
 • To explore the effect of C21 versus placebo as add on to SoC on inflammation. 	
 • Change from baseline in CRP at Day 15.

 • To explore the effect of C21 versus placebo as add on to SoC on lung injury. 	
 • Change from baseline in lactate dehydrogenase (LDH) at Day 15.

Primary estimand

All-cause mortality up to Day 60 defined as the time to day of death from any cause assessed for the intention-to-treat population with treatment as randomized, independent of treatment withdrawal or major protocol deviations according to the treatment policy, with subjects with no confirmed death before or at Day 60 being censored at day of withdrawal/Day 60 follow-up. The stratified log-rank test will be used to compare the treatments. The treatment difference will be expressed as a hazard ratio with 95% confidence intervals.

Key Secondary estimands

Time to sustained hospital discharge up to Day 60; The first occurrence of a score ≤ 2 whereafter the score stays ≤ 2 for the remainder of the 60 days trial period, assessed for the intention-to-treat population with treatment as randomized, independent of treatment withdrawal or major protocol deviations according to the treatment policy, with subjects who die prior to Day 60 being censored at Day 60 and subjects withdrawing due to other causes than death and not fulfilling the event being censored at the withdrawal day. The Kaplan-Meier difference in median time to sustained hospital discharge with 95% confidence intervals will be estimated.

Supplemental oxygen free days up to Day 29; For each subject the number of days between Day 1 and Day 29 with a score of ≤ 4 on the 8-point ordinal scale and with no documented use of COVID-19 related supplemental oxygen, assessed for the intention-to-treat population with treatment as randomized, independent of treatment withdrawal or major protocol deviations according to the treatment policy, with subjects who die prior to Day 29 being given the value -1 day and trial withdrawals prior to Day 29 due to other causes than death and not possible to follow-up being imputed using multiple imputation including assessments from day 1 to day 29. The Hodge-Lehmann median estimated of the difference in days between treatments with 95% confidence intervals will be estimated.

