10.12 Time to Sustained Hospital Discharge

Time to sustained hospital discharge is defined as the time to the date of discharge from initial hospitalization or re-hospitalization due to COVID-19 after which the subject is not re-hospitalized for COVID-19 related reasons.

If a subject dies, they will be censored at Day 60, if a subject withdraws (for reasons other than death) from the trial prior to observing the event (i.e. while still hospitalized) they will be censored at the time of withdrawal. If a subject has an event and subsequently withdraws (for reasons other than death), they will be treated as having the event in the analysis. Subjects who complete the trial without the event i.e. are still hospitalized at Day 60, will be censored at Day 60 in the analysis.

The calculation will be as follows:

$$\text{Time to sustained discharge (Days)} = \text{Date of Event or Censor} - \text{Date of first dose of IMP} + 1$$

where date of event for subjects who discharge will be the date of discharge from hospital (after which the subject is not re-hospitalized for COVID-19 reasons) as recorded on the Hospitalization CRF page. If a subject is re-hospitalized for COVID-19 reasons, the date of event will be the end date of this re-hospitalization (if no subsequent re-hospitalization for COVID-19 reasons).

Additionally, a sensitivity analysis will be performed where all re-hospitalizations are considered as COVID-19 related regardless of the investigator indicated cause. In the sensitivity analysis, date of event for subjects with missing data and no discharge record on the hospitalization form will be the relative day a value of ≤ 2 is achieved after which a subject has only imputed values of ≤ 2 for all subsequent visits. If subjects with imputed data have a recorded value of discharge on the hospitalization page and imputed data is ≤ 2 from this date of discharge, the recorded date of discharge will be used as event date in the calculation. If subjects with imputed data have a recorded value of discharge on the hospitalization page and any imputed data is > 2 from this date of discharge, time to sustained discharge will be the relative day a value of ≤ 2 is achieved after which a subject has an imputed value of ≤ 2 for all subsequent visits. If a subject with imputed data never observes the event they will be censored at Day 60.

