The statistical comparisons for the primary efficacy endpoint and the key secondary endpoints will be carried out in hierarchical order as below:

1. All-cause mortality up to Day 60
2. Time to sustained hospital discharge up to Day 60
3. Supplemental oxygen free days up to Day 29
4. Proportion of subjects free of respiratory failure at Day 15

5. Proportion of subjects discharged from hospital and free of supplemental oxygen at Day 15

This means that statistically significant results for the comparison in the higher rank are required to initiate the testing of the next comparison in the lower rank. All analysis will be performed in the above order, however if a statistical comparison is non-significant then all subsequent statistical analysis will be exploratory in nature and no formal conclusions will be drawn. In other words, if the test for endpoint 3 in the above order is non-significant, then endpoints 4 and 5 will be exploratory in nature.

Since a step-down procedure is used, each comparison will be tested at a significance level of 0.05 and an overall alpha level of 0.05 will be preserved.

All data collected during this trial regarding subject characteristics, efficacy and safety will be listed, unless otherwise specified. Screen failures will be excluded from all listings and tables if not otherwise noted. Listings will not show imputed data but will present data as reported.

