12.5.3.2 Time to Sustained Hospital Discharge

Time to sustained hospital discharge, will be defined as time to discharge after which no re-hospitalizations due to COVID-19 occur. Please refer to Section 10.12 for further details on this calculation.

Treatment groups will be compared using a stratified log-rank test adjusting for treatment, actual baseline disease severity and region. The size of the treatment effect will be estimated as a hazard ratio, obtained using a Cox proportional hazards regression model and the Cox regression model will include a factor for

randomized treatment, baseline disease severity and region. The estimated hazard ratios for each treatment group will be presented together with the corresponding 95% CI (based on Wald test).

Analysis will be illustrated using a Kaplan-Meier plot and the median time to hospital discharge will be estimated with 95% CIs for each treatment group. Subjects who die prior to Day 60 will be censored at Day 60 and trial withdrawals prior to Day 60 due to other causes than death without fulfilling the event will be censored at day of withdrawal. Subjects still in trial but not discharged from hospital at Day 60 will be censored at their Day 60 trial visit.

12.5.3.3 Oxygen Supplemental Free Days up to Day 29

Oxygen supplemental free days up to Day 29 will be defined as the number days for each subject with a score of ≤ 4 and no use of COVID-19 related supplemental oxygen. Refer to Section 10.13 for the derivation of number of oxygen free days.

Subjects who die prior to Day 29 will be given a value of -1 days in the analysis. Subjects who withdraw from the trial prior to Day 29 and have missing data will have their data multiply imputed as per Section 10.19.1. Subjects who chronically used supplemental oxygen prior to their COVID-19 illness will be considered oxygen free when they return to the same level of oxygen support they had been using prior to COVID-19.

Treatment groups will be compared using the Wilcoxon rank-sum test (using p-values) and the treatment difference will be expressed as the Hodges-Lehmann difference in median number of days with 95% CIs. All collected data post treatment will be used. Summary statistics for the number of oxygen free days will also be presented for each treatment group. A cumulative distribution plot of the number of oxygen free days by treatment arm will also be produced.

12.5.3.4 Subjects Free of Respiratory Failure at Day 15

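### The Appendix 5 derivation of time to sustained hospital discharge contradicts SAP 10.12: it drops the no-later-readmission condition and misnames a censoring date

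*SAP*

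**What the plan says.** The endpoint is listed in SAP 12.0 as "Time to sustained hospital discharge up to Day 60", second of five hypotheses.

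**Protocol Section 3** defines the event as "The first occurrence of a score ≤ 2 whereafter the score stays ≤ 2 for the remainder of the 60 days trial period". Protocol 9.3.3 adds that this means no COVID-19 readmission.

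**SAP 10.12** dates the event at "the date of discharge from hospital (after which the subject is not re-hospitalized for COVID-19 reasons"). If there is a COVID-19 readmission, the event moves to the end of that readmission. It continues: "Subjects who complete the trial without the event i.e. are still hospitalized at Day 60, will be censored at Day 60 in the analysis". Withdrawal while in hospital is censored at withdrawal.

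**SAP 12.5.3.2** repeats the no-readmission condition, sends the reader to 10.12 for the calculation, and says that "trial withdrawals prior to Day 60 due to other causes than death without fulfilling the event will be censored at day of withdrawal".

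**SAP Appendix 5, primary row**, says: "Date of event is the last date of discharge (for initial hospitalization or re-hospitalization for COVID-19 reasons) as recorded on the hospitalization form". A subject who has the event and then withdraws keeps the event. For a subject without the event by completion or discontinuation, "the subject is censored at date of completion/discharge (for reasons other than death"). For deaths: "Subjects are treated as worst case (Day 60 is value used in analysis").

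**SAP Appendix 5, sensitivity row**, also uses the last recorded discharge, now for readmission of any cause and for subjects with no missing data. Its censoring date is completion or Day 60.

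**The concern.** The last recorded discharge and a discharge that is sustained are different things when a readmission is still open. An open readmission has no discharge date on the form, so it cannot displace the earlier one. A program that takes the latest discharge date on the hospitalization form would then return a relapse without recovery as an early success.

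The endpoint is confirmatory if the mortality test succeeds, and it gates ranks 3 to 5. Appendix 5 is headed as derivation details, and the change history says it was added to summarize all efficacy derivations, so it is a natural place for a programmer to work from. No sentence in the SAP says which text prevails if the appendix and Section 10 differ.

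The sensitivity row, followed literally, would not expose the problem, because it uses the same rule for subjects with complete data.

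**Working it through.** The documents give no event count, sample size or power for this endpoint, so there is no figure to reproduce. The check applies both rules to the same patient histories.

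**Rule A (SAP 10.12).** Death: censored at Day 60. Otherwise, if the most recent COVID-19 stay ended in discharge, event on that date. If that stay is still open, censored at Day 60, or at withdrawal if earlier.

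**Rule B (Appendix 5 primary row, literal).** Death: censored at Day 60. Otherwise, if any discharge is recorded, event on the last recorded date. If none is recorded, censored.

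The histories are hypothetical. In the first five the subject is first discharged on Day 10, and all readmissions are for COVID-19.

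| History | Rule A | Rule B |
|---|---|---|
| Single stay | event Day 10 | event Day 10 |
| Readmitted Day 20, discharged Day 30 | event Day 30 | event Day 30 |
| Readmitted Day 20, in hospital at Day 60 | censored Day 60 | **event Day 10** |
| Readmitted Day 20, withdraws in hospital Day 25 | censored Day 25 | **event Day 10** |
| Readmitted Day 20, dies Day 40 | censored Day 60 | censored Day 60 |
| Never discharged, in hospital at Day 60 | censored Day 60 | censored Day 60 |

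The rules part in two of the six histories. Both are subjects readmitted for COVID-19, alive, and not discharged again before Day 60 or withdrawal.

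**Direction.** Under Rule A the subject in the third row stays in the log-rank risk set to Day 60 without an event. Under Rule B the same subject adds an event on Day 10 and leaves. On placebo this makes placebo discharge look faster and understates a C21 benefit. On C21 it overstates one.

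**How many.** The documents give no number. The SAP change history calls re-hospitalization rare but states no rate. As an assumption only, if 0.5% to 3% of the maximum 300 subjects were affected, the count would be 0.005 × 300 = 1.5 to 0.03 × 300 = 9. Zero is also possible.

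**Censoring clause.** The sentence opens with completion or discontinuation and closes with completion or discharge. It applies only to subjects without the event. Under Rule B a subject with a recorded discharge already has the event, so the clause reaches only subjects never discharged, who have no discharge date. The clause therefore cannot be applied as written to someone who withdraws before any discharge. SAP 10.12 and 12.5.3.2 both give the withdrawal day for that subject.

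**Sensitivity row.** For subjects with no missing data, 10.19.1 refers back to 10.12 and says a subject in hospital for a non-COVID-19 readmission is not counted as discharged during it. The row's last-discharge wording omits this for a readmission that is still open. Its censoring date does not share the discharge slip.

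**The case against.** The strongest reply is that the plan already has the right rule. SAP 10.12 states it in full. SAP 6.1, SAP 12.5.3.2, Appendix 1 and Protocol Sections 3 and 9.3.3 all require discharge to be sustained. The analysis section points to 10.12 and not to the appendix, and the row's own title contains the word *sustained*. This stands. A reader might infer that the plan itself scores relapsed patients as successes, but the documents do not support that: it would happen only if a summary cell were programmed over several consistent sections.

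A reader might also infer that the censoring clause turns a readmitted subject into a success, or censors that subject at the first discharge. Neither follows. Censoring cannot create an event and, on the literal reading, the readmitted subject already has one, so the clause never applies. The word looks like a slip for discontinuation.

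Finally, one might infer a systematic bias against C21, or attach a loss of power to it. That would need a discharge hazard ratio, discharge rates by arm and a count of affected subjects, none of which the documents give.

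The reply does not remove the contradiction. The literal row gives a different event status from 10.12, and nothing in the SAP ranks one text above the other.

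**Conclusion.** The Appendix 5 rows are wrong as written and contradict SAP 10.12, SAP 12.5.3.2 and the protocol on a key secondary endpoint. The primary row lacks the condition that no COVID-19 re-hospitalization follows and, separately, names an unusable censoring date. The sensitivity row lacks the matching condition for readmission of any cause.

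The consequence is limited. It depends on Appendix 5 being followed in preference to 10.12, and it matters for confirmatory inference only if the mortality test succeeds. Any bias could run either way, and its size cannot be derived from the documents. This is a contradiction to be corrected, not evidence that the intended analysis is unsound.

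**What to change.** Before database lock, amend three places in SAP Appendix 5:

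1. **Primary row, event.** Date the event at a discharge not followed by any COVID-19 re-hospitalization up to Day 60. State that a re-hospitalization still open counts as no event: censor at Day 60, or at the day of withdrawal if the subject withdraws while in hospital.
2. **Primary row, censoring.** Replace completion/discharge with Day 60/withdrawal.
3. **Sensitivity row.** Make the same alignment for readmission of any cause, consistent with 10.12 and 10.19.1.

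The cost is a few lines of SAP text. No new data are needed and the estimand does not change. If programming has begun, run the histories above as test cases to confirm that the code follows 10.12.

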8.3. Survival and Hospitalization

Data on survival, hospital discharge and hospital re-admissions will be collected at each visit from Day 2 (Visit 3) to Day 60 (end-of-trial). Information on the hospital setting, including intensive care unit (ICU), high flow oxygen device use, ventilator use (Non-invasive, Invasive or ECMO) will be collected.

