9.2.2 Other Secondary Efficacy Endpoints

- Proportion of subjects discharged from hospital and free of supplemental oxygen at Days 8, 22 and 29.
- Proportion of hospitalized subjects on non-invasive, invasive mechanical ventilation, extra corporeal membrane oxygenation (ECMO) or supplemental oxygen use at Days 8, 15, 22, 29 and 60.
- Proportion of subjects in each category of the 8-point ordinal scale at Days 8, 15, 22, 29 and 60.

- Duration of hospitalization, including re-hospitalization, up to Day 60.
- Proportion of subjects needing intensive care unit stay at Days 8, 15, 22, 29 and 60.
- Duration of intensive care unit stay, including re-admission, up to Day 60.
- Proportion of subjects on invasive mechanical ventilation or ECMO at Days 8, 15, 22, 29 and 60, and duration of use up to Day 60.
- Proportion of subjects free of respiratory failure at Days 8, 22, 29 and 60, and respiratory failure free days up to Day 60.
- All-cause mortality up to Days 8, 15, 22 and 29.
- Change from baseline in peripheral capillary oxygen saturation (SpO_2) / fraction of inspired oxygen (FiO_2) at Day 15.

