10.16 Duration of ICU Stay

The duration of ICU stay will be calculated as

$$\text{Duration (days)} = \text{End date of ICU stay} - \text{Start date of ICU stay} + 1$$

The duration of multiple ICU stays in the period will be summed together to derive the overall duration of ICU stay. If a subject dies or discontinues prior to the end of the ICU stay or the subject died and had no ICU stay, the subject will be considered in the ICU from the date of death/discontinuation through Day 60. For subjects who discontinue the trial in hospital but not in ICU or discontinue following discharge they will not have any imputed additional days added to the number of days recorded on the available assessments. If the start date of the ICU stay is prior to treatment start, the treatment start date will be used as the ICU start date in the above derivation. For subjects with no ICU stay a value of 0 days will be used in the analysis. Note that ICU stays associated with re-admission for non-COVID reasons should not contribute to the duration.

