10.17 Duration of Invasive Ventilation or ECMO

The duration of invasive ventilation or ECMO use will be calculated as

$$\text{Duration (days)} = \text{End date of use} - \text{Start date of use} + 1$$

The duration of multiple invasive ventilation or ECMO use will be summed in the period to derive the overall duration. For subjects who die they will be considered on invasive ventilation or ECMO from date of death through Day 60. Subjects who discontinue the trial prior to discharge from hospital with last ordinal scale assessment of 7 will be considered on invasive ventilation or ECMO from date of discontinuation through Day 60. Subjects who discontinue the trial in hospital with last known status on the 8-point ordinal scale of ≤ 6 or subjects who discontinue following discharge will be considered not on invasive ventilation or ECMO through Day 60 and will have no additional days added to the number of days recorded on the available assessments. For subjects with no invasive ventilation/ECMO use a value of 0 days will be used in the analysis.

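### ICU and invasive ventilation/ECMO durations add up inclusive record lengths with no rule for shared or overlapping dates, so some days count twice and a total can exceed 60

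*SAP*

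**What the plan says.** SAP 9.2.2 lists, among the other secondary endpoints, "Proportion of subjects on invasive mechanical ventilation or ECMO at Days 8, 15, 22, 29 and 60, and duration of use up to Day 60", and also the duration of ICU stay up to Day 60.

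For ventilation/ECMO, SAP 10.17 sets each use at end date minus start date plus 1 and then states: "The duration of multiple invasive ventilation or ECMO use will be summed in the period to derive the overall duration". Deaths get additional days: "For subjects who die they will be considered on invasive ventilation or ECMO from date of death through Day 60". Subjects who leave the trial in hospital with a last ordinal score of 7 are handled in the same way from the date of discontinuation. Appendix 5 condenses this to "End date of use-start date of use +1; sum together; discontinue while on, considered on from date of discontinuation".

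For ICU, SAP 10.16 uses the same inclusive formula: "The duration of multiple ICU stays in the period will be summed together to derive the overall duration of ICU stay". After death, or after discontinuation during an ICU stay, "the subject will be considered in the ICU from the date of death/discontinuation through Day 60". Appendix 5 has "End date of ICU stay -start date +1; sum individual together".

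Protocol 8.3 says that "ventilator use (Non-invasive, Invasive or ECMO) will be collected". It does not say how the records are laid out. SAP 12.5.4 compares both durations between arms by the Wilcoxon rank-sum test.

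**The concern.** End minus start plus 1 is correct for one isolated interval. It fails when intervals touch or overlap, because a date that closes one interval and opens the next lies in both. Three situations produce this:

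- a record that ends on the date of death or discontinuation, which is also the first day of the assigned period;
- two consecutive records that share a transfer date;
- two records that run at the same time.

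Neither 10.16, 10.17 nor Appendix 5 merges intervals, drops a shared date or limits the total. The SAP does take care over this elsewhere: in 10.14, the respiratory-failure-free days between discharge and re-admission are a plain date difference without the plus 1, so the re-admission date is left out.

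At stake are summary statistics that can exceed the observation period, and ranks that depend on how records were split and not on time in the ICU or on support.

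**Working it through.** The plan gives no numerical result for these durations, so there is no figure to reproduce. The check applies the written rule to hypothetical episodes and compares it with a count of distinct calendar days.

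**Inputs**
- Length of a record: end − start + 1, summed over records (SAP 10.16, 10.17, Appendix 5).
- Days added for a death on Day d: 60 − d + 1 (SAP 10.16, 10.17). The same applies to discontinuation in ICU or on support.
- Follow-up: Day 1 to Day 60.

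**1. Date shared with the period after death** (assumes that the support record is closed on the date of death)
- Ventilated Days 1-20, death on Day 20: (20 − 1 + 1) + (60 − 20 + 1) = 20 + 41 = 61. Distinct days: 60.
- Ventilated Days 5-20, death on Day 20: 16 + 41 = 57. Distinct days: 56.

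The excess is one day. With one continuous episode, 61 is the maximum, and it needs support from Day 1.

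**2. Date shared by two records**
- ICU Days 1-10, then 10-20: 10 + 11 = 21. Distinct days: 20.
- Ventilation Days 5-12, then ECMO Days 12-20: 8 + 9 = 17. Distinct days: 16.
- ICU Days 1-30, then 30-60: 30 + 31 = 61. Distinct days: 60.

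The excess is one day per shared date. For a surviving subject's ICU duration, passing 60 needs a nearly continuous stay.

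**3. Concurrent records** (assumes that the CRF holds ventilation and ECMO as separate records with their own dates)
- Ventilation Days 6-45, ECMO Days 10-34: 40 + 25 = 65. Distinct days: 40.

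The excess is the whole overlap, 25 days.

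**4. Where deaths fall under the same rule**
- Ventilation Days 3-30, ECMO Days 8-27, death on Day 30: 28 + 20 + 31 = 79. Distinct days: 58.
- Death on Day 30, never ventilated: 60 − 30 + 1 = 31.
- Survivor ventilated Days 3-45 in one record: 43, with no day counted twice.

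**The case against.** Several points on the other side stand. The SAP treats invasive ventilation and ECMO as one state (ordinal score 7 and one combined endpoint), so a use in 10.17 can be read as one spell in that state whatever the device. On that reading the 65-versus-40 example does not arise, and the documents cannot settle it because CRF version 3.0 is not among them. A sensible programmer might also merge intervals unprompted. The endpoints are non-key and outside the testing hierarchy. Protocol exclusion criteria 7 and 8 keep out subjects with recent or imminently expected invasive ventilation or ECMO, so few will have long spells starting near Day 1. Subjects with no use score 0, and one extra day among a few users barely moves a rank sum.

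This limits the size but does not supply the missing rule. The shared date at death needs no assumption about separate device records, only that support is recorded up to that date. The situation is not remote: Protocol 2.2 reports that all four phase 2 deaths were in patients who needed mechanical ventilation.

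A reader might infer more, namely that a survivor can rank below every death and so breach the SAP's worst-case treatment of deaths. The documents do not support that. Deaths follow the same unlimited sum, and the two-device death in step 4 scores 79, above the survivor at 65. The worst-case statement in SAP 10.19 concerns the days after death; it does not promise that each death outranks each survivor. Survivors can already outrank some deaths with no double counting (43 against 31 in step 4), because deaths add days to recorded use and are not set to a fixed worst value.

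**Conclusion.** The point holds as a gap in the derivation rule. Followed as written, SAP 10.16, 10.17 and Appendix 5 count a shared date twice and can give a value above 60 for a 60-day period. The excess is one day per shared date. It becomes the full length of the overlap only if ventilation and ECMO are held as separate concurrent records, which is an assumption. The expected effect on the two rank-sum comparisons is small, since probably few subjects are affected; no effect on a p-value or estimate can be computed from the documents. The primary endpoint and the key secondary endpoints do not use these derivations. How deaths should rank against survivors is a separate question, and this point does not settle it.

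**What to change.** In SAP 10.16, 10.17 and Appendix 5, define each duration as the number of distinct trial days from Day 1 to Day 60 on which the subject was in the ICU (or, for the other endpoint, on invasive ventilation or ECMO). State that days assigned after death or discontinuation belong to the same union of intervals. The maximum is then 60 by construction, so no separate cap is needed. The examples above become 60, 56, 20, 16, 60, 40 and, for the two-device death, 58.

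The cost is one sentence in each place and a standard interval-union step in the programming, with no new data. The change leaves the 43-against-31 ordering as it is. If the sponsor intends deaths to rank worst on these endpoints, that needs its own statement.
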